During year 2, a randomized study (3 intervention and 3 control ASPs) will be implemented to test the feasibility of the intervention approach (N=200 youth). A 12-week follow-up, will test the sustained effects of the social climate intervention on ASP PA climate, youth PA affect, cognitions, behaviors, and BMI

Figure 2. Project Timeline

YEAR 1	YEAR 2
April-Sept 2014 - Interviews/Focus Groups - Observations - Intervention development - ASP program recruitment - Hire and Train Staff	Aug-Oct 2015 - Intervention/Measurement Staff Training - Baseline Data Collection (2 ASPs) - Intervention Implement cohort 1
Sept-Dec 2014 - Pilot Baseline Data Collection - Pilot Intervention (1 ASP vs. 1 control)	Oct-Dec 2015 - Baseline Data Collection for cohort 2 (2 more ASPs) - Intervention Implement (cohort 2)
Feb-Apr 2015 - Post-measures in Pilot ASPs - Data cleaning - Hire Project Staff for Y2	Jan-March 2016 - Post-measures for cohorts 1 and 2 - Baseline data collection for cohort 3 (2 ASPs) - Intervention implement (Cohort 3)
April-July 2015 -Data analysis - Revisions to intervention and measurement - ASP Recruitment for Y2	April-May 2016 - Post-measures cohort 3 - Data Management/ Analysis -Manuscript Preparation

Primary Aim 1 (COMPLETED PHASE 1): Interviews/Focus Groups and Youth Survey

Measures. During year 1, we conducted staff interviews (SIs) and youth focus groups (FGs; youth ages 9-14) in ASP sites to assess 1) key physical (e.g., equipment allocation), structural (e.g., PA preferences, activities offered), interpersonal (e.g., peer behaviors), and intrapersonal supports (e.g., social skills) needed to promote and support a social affiliation orientation towards PA (friendship, group belonging, and staff connection goals), 2) program barriers impeding the development and achievement of these social goals, and 3) input on the design and feasibility of initially- developed program components. Through content analysis (NVivo) we identified key themes related to improving social affiliation that were used to inform the development and implementation of the social climate intervention.

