to intervention protocol an internal process evaluation will be implemented each week for corrective feedback and adjustment as needed, and a booster training session for all staff will be implemented at mid-point. There is little-to-no communication across ASP sites (each site has their own staff and serve youth from distinctly separate schools), however to limit cross-contamination between study sites we will enlist the help of the program directors who have previous experience with other RCTs and possess a strong understanding of the importance of having distinct intervention and control conditions. These strategies have been highly successful in our previous studies.²⁵⁻²⁷

Study Measures

All study measures will be collected by trained and certified staff blind to group assignment. The PI will hire a Program Coordinator to assist with oversight and training of measurement staff. Measurement certification entails reviewing protocols and demonstrating agreement with the Coordinator on anthropometrics, systematic observations, survey protocols, and PA assessments. Our team has experience developing and using these protocols in large scale studies.²⁵ **See Appendices for all measures.**

Primary Aim 2. Feasibility

To test the feasibility of intervention implementation, **process evaluations** that monitor dose and fidelity will be conducted within both the intervention and control conditions once a week by an independent process evaluator for the duration of the program (**see Appendix B**). Through observation and use of a quantitative checklist and rating scales, the process evaluator will assess whether there are any changes in the structure, delivery, or climate of the control condition (e.g., whether youth are consistently provided at least 1 hour of daily free play), and whether the social climate of intervention ASPs achieve the program's essential elements.

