This proposal is a feasibility test of the social climate intervention and will gauge a plausible effect size of the program for a larger R01 application. To that end, we will examine several subjective and objective markers of program success such as changes in targeted social mechanisms within youth and the ASP climate, and explicit PA outcomes. We will also explore the potential effects of the intervention on youth BMI. Although only minimal change in BMI would be plausible given the length of the current proposal, our findings will have implications for impacting BMI as the targeted outcome of a larger R01 trial.

Primary Aim 1. (ADDRESSED). The first aim of the study is to conduct qualitative interviews with program staff and youth to identify conceptual constructs most relevant for fostering youth PA affiliation orientation. Interviews and focus groups will be transcribed, coded, and analyzed (QSR NVivo) to identify common themes for these study goals. A coding scheme composed of “levels” of categorization or manageable “themes,” will be developed to guide the manner in which the qualitative data will be analyzed. Ultimately, these themes will be used to summarize the data. Data will be coded by two coders and inter-rater reliability estimates will be assessed. Prior to analysis, raters will meet to discuss each coding disagreement until consensus is met regarding final codes. The PI has extensive experience in using QSR NVivo to conduct content analysis of themes (see our previous work).²⁸

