Primary Aim 2. The second primary aim of the study is to assess whether youth in the intervention demonstrate greater change in the 3 PA social affiliation mechanisms from baseline to post-intervention. Gains in these social mechanisms will be assessed with repeated measures ANCOVA models in which time (baseline to end of program and baseline to post-intervention) is a within subject factor and treatment is a between subjects factor for social mechanism variables measured in both conditions. Analyses will control for demographics, baseline BMI, and any other variables for which there are baseline differences between treatment and control groups (e.g., PYD, depression). To examine overall changes in social mechanisms within the intervention alone, similar repeated measures ANCOVAs will be used, with the between subjects treatment factor dropped. The test of interest will be the within subjects factor of time, with affiliation goals expected to improve over time. Process Evaluation, used to assess the quantity (dose) and quality (fidelity) of program implementation, will also serve as feasibility assessments. Our group has extensive experience with “dose-response” analyses.²⁷ Weekly observational assessments of program facilitation, using standardized ratings developed for other studies,¹⁰¹⁻¹⁰³ will be reduced to a total score, indicating overall fidelity to the activity observed.

Secondary Aims. **Secondary Aims 1 and 2** tests the a-priori hypothesis that youth in the intervention (vs. comparison) will have greater improvements in PA affect, cognitions, and MVPA and healthier BMI (z-score) trajectories (e.g., slight reduction; less increase) from baseline to post-intervention. This study will also provide us with information on the effect size that might be expected to power an efficacy trial after completion of the R21 project. Greater improvements will be assessed with several repeated measures ANCOVA models in which time (baseline to post-) is a within subject factor and treatment is a between subjects factor for PA variables measured in both conditions. Analyses will control for demographics (and BMI for PA outcomes) and other variables for which there are baseline differences between treatment and control groups. Multiple imputation protocols^{104,105} will be used to address missing accelerometer data (see our previous work).²⁵

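### Six whole afterschool programs are randomised, but the youth analyses have no program term, so between-arm precision is overstated if change is correlated within programs

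*Combined protocol and SAP*

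**What the plan says.** - **Design.** Section D (Study Design; Targeted Population, Recruitment, and Retention) allocates six ASPs in year 2, three to each condition, after baseline measurement, with a target of 200 youth. Figure 2 brings the ASPs in as three cohorts of two. No section says how allocation was arranged across cohorts.
- **Primary Aim 2 (Section E).** Social mechanism variables are analysed by repeated-measures ANCOVA. On the arm comparison the plan says that "treatment is a between subjects factor for social mechanism variables measured in both conditions". Two contrasts over time are planned in the same model: "time (baseline to end of program and baseline to post-intervention) is a within subject factor". The covariates are demographics, baseline BMI and variables found to differ at baseline; ASP is not listed. A further model drops the treatment factor: "To examine overall changes in social mechanisms within the intervention alone", the effect of time is tested.
- **Secondary Aims 1 and 2 (Section E).** The same form applies to activity outcomes and BMI z-score; "treatment is a between subjects factor for PA variables measured in both conditions".
- **Secondary Aim 3 (Section E).** A multiple-mediator path model with bootstrapped indirect effects. No cluster structure is stated.
- **Use of the results (Section E).** The study "will gauge a plausible effect size of the program for a larger R01 application" and is to supply "information on the effect size that might be expected to power an efficacy trial after completion of the R21 project".

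Nothing in the document adds a site effect, multilevel model, cluster-robust variance, analysis of site means, ICC, design effect or degrees-of-freedom rule for the youth outcomes.

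**The concern.** Treatment varies only between ASPs, so the arm comparison rests on six randomised units. A model with treatment as a between-subjects factor and no site term takes its error from about 200 youth as if they were independent.

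The parameter that matters is the ICC of the covariate-adjusted change. Stable differences between sites cancel in the change and do no harm; a shared change within a site does not cancel. Shared change is plausible on the protocol's own account: the section on potential challenges says "each site has their own staff and serve youth from distinctly separate schools", and the Overview of Intervention aims at staff and peer behavior, program structure and the physical setting, all of which operate on a site as a whole.

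At stake are the p-values and intervals for the youth-reported feasibility criterion (the first of four under Primary Aim 2, with no significance threshold named) and for activity affect, cognitions, MVPA and the exploratory BMI outcome. The other three feasibility criteria do not use these models. The main practical harm is that an effect size would go into the planning of a larger trial with more apparent precision than six sites can give.

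**Working it through.** There is no stated power, ICC or precision figure to reproduce.

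**Inputs from the document.** 200 youth; 3 + 3 ASPs; so n = 100 per arm and m = 200/6 = 33.3 youth per ASP.

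**Assumptions.** Two-sided 5% level and 95% intervals (the plan states neither); similar site sizes; ICC of change from 0 to 0.10; change scaled to a total SD of 1. Widths below are therefore in SDs of change, not the cross-sectional SDs listed under Study Measures.

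**Step 1, true variance.** Design effect DE = 1 + (m − 1) × ICC. The variance of the arm difference is 2 × DE/100.

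**Step 2, variance the youth-level model reports.** Its expected residual variance is E = ICC × (100 − 33.3)/99 + (1 − ICC).

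**Step 3, type I error.** r = √(DE/E); error = 2 × [1 − Φ(1.96/r)]. At ICC 0.05: DE = 2.62, E = 0.984, r = 1.63, 1.96/1.63 = 1.20, error 0.230.

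**Step 4, half-widths.** Planned: t(198) = 1.972, and 1.972 × √(2/100) = 0.28. Clustering alone: 0.28 × √DE. Site-based: six site means less two arm means leave 4 df, and t(4) = 2.776, giving 2.776 × √(2 × DE/100).

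| ICC of change | DE | Error, formula | Error, simulated | Half-width planned | Clustering alone | Site-based, 4 df |
|---|---|---|---|---|---|---|
| 0 | 1.00 | 0.050 | 0.050 | 0.28 | 0.28 | 0.39 |
| 0.01 | 1.32 | 0.089 | 0.088 | 0.28 | 0.32 | 0.45 |
| 0.02 | 1.65 | 0.128 | 0.125 | 0.28 | 0.36 | 0.50 |
| 0.05 | 2.62 | 0.230 | 0.226 | 0.28 | 0.45 | 0.64 |
| 0.10 | 4.23 | 0.349 | 0.344 | 0.28 | 0.57 | 0.81 |

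The simulation used 100,000 null trials per setting with 33 youth per site. A t-test on the six site mean changes (4 df) rejected in 0.049 to 0.051. A nominal 95% youth-level interval covers in about 91%, 87%, 77% and 66% of trials at ICC 0.01 to 0.10.

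**Variations**
- Site sizes from 20 to 46: youth-level error 0.090, 0.132, 0.236 and 0.356; site-mean test 0.049 to 0.050.
- Stable site ICC 0.10 but ICC of change 0 (20,000 trials): youth-level error 0.049, confirming that only correlated change matters.
- Two-stage covariate-adjusted site means (20,000 trials per ICC): 0.050 to 0.051.

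**Pairing within cohort** (ranges run from ICC 0.01 to 0.10):

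| Share of site variance carried by cohort | Youth-level error | Unpaired 4-df error | Paired 2-df half-width |
|---|---|---|---|
| 0 | 0.089 to 0.345 | 0.050 to 0.051 | 0.70 to 1.25 |
| 0.5 | 0.069 to 0.226 | 0.041 to 0.026 | 0.66 to 0.98 |
| 1 | 0.049 to 0.043 | 0.033 to 0.008 | 0.61 to 0.58 |

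The paired 2-df test holds 0.049 to 0.051 throughout. In these settings it is narrower than the unpaired interval only when cohort carries all the site variance and the ICC is 0.05 or more (0.60 against 0.64; 0.58 against 0.81). If allocation was unrestricted but cohort matters (share 0.5 or 1), the unpaired 4-df test rejects in 0.050 to 0.057.

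**Intervention-only time test.** Generalised to other ASPs, the youth-level error is 0.088, 0.125, 0.223 and 0.344. Read as a statement about these three sites, it is 0.050 to 0.043. A test on the three site means (2 df) holds 0.049 to 0.052.

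**Reliability of the ICC estimate.** With six sites, the ANOVA estimate is zero or negative with probability P(F(4,192) ≤ 1/(1 + 33 × ICC/(1 − ICC))): 44% at ICC 0.01, falling to 7% at 0.10.

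**The case against.** **It is a feasibility study.** Section E says so, the point estimate is sound when sites are similar in size, and no significance threshold is set. This limits the consequence, but Section E still specifies between-arm tests, presents Secondary Aims 1 and 2 as an a priori hypothesis, and carries the effect size forward. Its uncertainty has to be right.

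**Allocation may have been paired.** Figure 2 starts cohort 1's intervention before cohort 2's baseline, and randomisation follows baseline, so ASPs were probably allocated two at a time; one per arm in each cohort would give 3:3. This is a fair point. With half the site variance in cohort, the error is 7% to 23% rather than 9% to 34%, and the unpaired 4-df test becomes conservative. With all of it in cohort, there is no inflation. The plan states neither the pairing nor anything that would make that extreme case likely.

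**The widening is not all due to the ICC.** Correct. Even at ICC 0 the site-based half-width is 0.39 rather than 0.28, which is the price of 4 df; at ICC 0.01 most of the widening comes from this.

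**Fewer youth may be analysed.** At 25 per ASP the error would be about 8%, 11%, 19% and 30%. The section on potential challenges expects good retention, and the conclusion is unchanged.

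**An ICC from six sites is a poor estimate.** This stands, and it should be reported with that caution.

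**Conclusion.** The concern holds. Followed as written, the youth analyses ignore the unit of randomisation, and between-arm p-values are too small and intervals too narrow whenever the allocation leaves site-level variance of change in the arm comparison. Without shared cohort variance, the true error of a nominal 5% test is about 9% at an ICC of change of 0.01 and about 34% at 0.10. The range rests on an assumed ICC, an assumed 5% level and about 33 youth per site. At an ICC of change of zero the planned test keeps its level. The intervention-only time test is affected only if its result is generalised beyond the three sites. The correction should be made before the youth outcomes are analysed.

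**What to change.** 1. For each youth outcome and each planned contrast (Primary Aim 2: baseline to end of program and baseline to post-intervention; Secondary Aims 1 and 2: baseline to post), compare covariate-adjusted ASP mean changes, three against three, by a t-test with 4 df. Alternatively, fit a mixed model with ASP and ASP-by-time effects whose df stay tied to the number of ASPs even when the site variance is estimated as zero. Fixed ASP effects alone will not do, because treatment is constant within an ASP.
2. State how ASPs were allocated across the three cohorts. If they were paired, pre-specify either the unpaired 4-df test (valid, possibly conservative) or the paired 2-df test. This is a choice about precision.
3. Analyse the intervention-only time test on the three site means (2 df), or report it descriptively for those sites.
4. Make the mediation analysis respect clustering, or report it descriptively. Carry the site structure into the multiple imputation of accelerometer data as well.
5. Report each effect size carried forward with its site-based interval, the SD of change and the ICC, noting how poorly six sites estimate the ICC.

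The cost is plan wording and some extra analysis. Intervals widen, fewer results reach significance, and the three-site time test becomes close to descriptive. No new data or participants are needed.

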Physical inactivity has been identified as a primary contributor of childhood obesity and related diseases, with underserved youth (minority and low-income status) at greatest risk of inactivity and its health consequences. However, physical activity (PA) interventions have attained limited-to-no sustained behavior change and thus, have rarely affected targeted physiological or anthropometric health outcomes. Despite substantial research noting the importance of social influences and goals (e.g., being with, and making friends) on PA motivation and participation, PA-based interventions have almost exclusively emphasized approaches centered on constructs related to physical ability (e.g., mastery, self-efficacy). To date, little research has focused on understanding the contributions that social goal orientations and need for connectedness make toward promoting sustained youth PA. We argue that during adolescence, when orientation towards social relationships is strongest, the desire for social connections is a primary goal of action underpinning youth PA behavior and thus, a key mechanism to target for sustained behavior change. Thus, the proposed study will address limitations in previous research by targeting the social mechanisms needed within afterschool programs (ASPs) to promote sustained increases in youth PA. Application of social development research, Achievement Goal Theory, and Self-Determination Theory provides the conceptual framework for addressing key social mechanisms: 1) Friendship (and the development of PA-based social skills); 2) Group Belonging (peer connection), and; 3) Connection with ASP Staff. Primary components of the study include “Get to know you” sessions aimed at providing youth guided social opportunities to foster friendship-building skills, and to promote acceptance, cooperation, contribution, and friendship affiliation, and infusing a novel socially-oriented PA curriculum within ASP free play sessions. A total of 8 afterschool programs that serve a primarily underserved population will be asked to participate in the program. During the spring of year 1, (phase 1), staff and youth interviews, youth surveys, and systematic observations of ASP sites were conducted to develop the program curriculum and staff training (previously approved by IRB – **Pro00031648**). During this upcoming Fall of year 1 we plan to test our curriculum during an 8-week pilot (1 intervention and 1 control ASP (N=60 youth). During year 2 (Fall, 2015), after addressing measurement and/or implementation challenges identified in our Y1 pilot, a randomized study (3 intervention and 3 control ASPs) will be implemented to test the feasibility of the intervention approach (N=200 youth). Feasibility of our intervention should demonstrate that intervention youth report greater perceived connectedness and affiliation goal orientation toward PA from baseline to post-intervention. Observations of ASPs will test changes in the social climate from pre- to post-intervention and process evaluation will assess dose and fidelity. It is hypothesized that: 1) youth in the intervention (vs. comparison) will demonstrate greater improvements in positive PA affect, cognitions, and behaviors, and BMI from baseline to post-intervention, and; 2) targeted social mechanisms will mediate the effects of the intervention on changes in PA outcomes.

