
B. Specific Aims

Physical inactivity has been identified as a primary contributor of childhood obesity and related diseases,¹⁻⁷ with underserved youth (minority and low-income) at greatest risk of inactivity and its health consequences.^{6,7} However, physical activity (PA) interventions have attained limited-to-no sustained behavior change and thus, have rarely affected targeted physiological or anthropometric health outcomes.⁸⁻¹² Extensive research on sport participation shows highly engaged youth report an affiliation orientation towards PA, identifying social reasons and goals (e.g., being with, and making friends) as their primary motivations for participation, and defining PA competence as achieving these social goals.¹³⁻¹⁵ Despite substantial research noting the importance of social goals on PA-based self-determined motivation¹⁶⁻¹⁸ and participation,¹⁹⁻²¹ PA-based interventions have almost exclusively emphasized approaches centered on constructs related to physical ability (e.g., mastery, self-efficacy).²² To date, little research has focused on understanding the contributions that affiliation orientations (social goals) make toward promoting sustained youth PA.^{23,24} We argue that adolescents' desire for social connections is a primary goal of action underpinning their PA behavior and thus, a key mechanism to target for sustained behavior change. The Active by Choice Today (ACT) program, conducted by our investigative team is one of the first afterschool programs (ASPs) to implement a climate-based intervention based on Self-Determination theory which shows significant improvements in PA in underserved youth.²⁵⁻²⁸ However, limited sustained effects found post-intervention, and data from interviews with ACT staff and youth²⁸ which indicated the presence of several interpersonal barriers (e.g., cliques, teasing) to program effectiveness, suggests additional social climate components still need to be addressed. Systematic observations of ASPs using an observational tool that the PI has developed and tested²⁹⁻³¹ and additional interviews conducted with ASP staff and youth further suggests that targeting youth social goals (e.g., building friendships through PA) and social competencies (e.g., friendship-building skills) may be particularly effective for increasing and *sustaining* the PA of underserved youth. Thus, the proposed study aims to test the feasibility of expanding on the social climate approach of ACT to include three key "PA affiliation orientation" elements for increased and sustained youth PA: 1) Friendships (conceptualizing PA success/competence in terms of having close, mutual relationships with other individuals); 2) Group Belonging (defining competence in terms of feeling liked and accepted by peers), and; 3) Staff Acceptance/Connection (viewing success as feeling connected to, supported, and encouraged by staff).¹³⁻¹⁵ These elements have not been explored in prior research and we believe by enhancing ACT to include them in the resultant ACT2-Connect intervention will lead to sustained positive PA affect, cognitions, and behaviors in underserved youth. Comparison of ASPs receiving the 8-week "Connect" intervention (N=3 ASPs) with ASPs randomized to receive the general ASP curriculum (control condition; N=3 ASPs) will yield preliminary data on the effectiveness of social mediators for improving moderate-to-vigorous (MV)PA and preventing obesity among at-risk youth that can inform future intervention design and youth programming policy. Results of this proposed project will provide the basis for conducting a large scale efficacy trial.

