
Specific Objectives:

Develop and test the feasibility of the "Connect" intervention for increasing PA affect, cognition, and MVPA of underserved youth within ASPs. The effects of the intervention on youth body mass index (BMI) trajectories will also be explored and will have implications for impacting BMI as the targeted outcome of a larger R01 trial.

Primary Aims (Program Development and Feasibility):

1. Through qualitative interviews with staff and youth at ASP sites serving at-risk youth assess:
a) conceptual constructs most relevant for facilitating and supporting youth PA social goals; b)

barriers present within ASPs for meeting PA social goals (addressed in Phase 1, previously approved by IRB: Pro00031648).

2. Explore the feasibility of the Connect program. The Connect program will be documented to be feasible as shown by: 1) youth's greater perceived connectedness and PA affiliation goal orientation from baseline to post-intervention; 2). changes in targeted social climate components from baseline to post-intervention as measured by systematic observations, 3) staff perceptions of feasibility and acceptability of program as measured by a baseline and follow-up readiness assessment, and; 4) adequate dose and fidelity of program implementation as indicated by weekly process evaluations.

Secondary Aims (Document the preliminary impact of the Connect program on PA outcomes):

1. Assess whether youth in the social climate program (vs. comparison) demonstrate greater increases in positive PA affect, cognitions, and MVPA from baseline to 12-weeks post-intervention.
2. Explore whether youth in the social climate program (vs. comparison) demonstrate healthier BMI trajectories (e.g., slight reduction) from baseline to 12-weeks post-intervention.
3. Assess whether changes in targeted social mechanisms will mediate the effects of the intervention on changes in PA affect, cognitions, and MVPA from baseline to post-intervention.

C. Background and Significance

Physical Activity for the Prevention of Obesity and Related Disease

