Secondary Aim 3 explores whether changes in youth PA social orientations mediate the effect of the intervention on changes in adolescent PA outcomes. This hypothesis will be tested with a

multiple mediator model (estimated path model) where the indirect effect of the program on PA through social mechanisms will be examined. Bootstrapped estimates of the mediated effect will be examined in line with recommendations from methodological research.^{106,107} Both the total indirect effect of all variables together and specific mediated effects of each variable will be examined.

F. Human Subjects

Protection of Human Subjects

Risks to the Subjects

Human Subjects involvement and Characteristics. Subjects will be healthy male and female adolescents and adults. To be eligible, adolescents must 1) be currently enrolled in the afterschool program, 2) have parental consent to participate, and 3) agree to study participation and random assignment, and 4) be available for baseline and post-intervention measurement. Adolescents will be excluded from participation if 1) have a medical condition that would interfere with the prescribed physical activity intervention plan, 2) are developmentally delayed such that the intervention materials will not be appropriate or, 3) are in treatment for a psychiatric disorder. To be eligible, adults must 1) be part of the afterschool staff, 2) have no medical condition or disorder that would limit participation, 3) be available and able to participate in the interviews and/or the intervention phase for the study period.

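### Feasibility criterion 1 names no comparator, and the plan does not say whether the two-arm or the intervention-only analysis decides it

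*Combined protocol and SAP*

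**What the plan says.** Section B, Primary Aims, item 2 lists four things that will show the program to be feasible. The first is youth's "greater perceived connectedness and PA affiliation goal orientation from baseline to post-intervention". The opening abstract words it similarly: "Feasibility of our intervention should demonstrate that intervention youth report greater perceived connectedness and affiliation goal orientation toward PA from baseline to post-intervention". Neither sentence names a comparator. The Secondary Aims that follow in Section B do. Item 1 reads "Assess whether youth in the social climate program (vs. comparison) demonstrate greater increases in positive PA affect, cognitions, and MVPA", and item 2, on BMI, carries the same parenthesis.

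Section E, Primary Aim 2 restates the aim as a larger change among intervention youth and gives two analyses:

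- A repeated measures ANCOVA in which time is within subjects and "treatment is a between subjects factor for social mechanism variables measured in both conditions".
- A second set of models: "To examine overall changes in social mechanisms within the intervention alone, similar repeated measures ANCOVAs will be used", this time without the treatment factor. For these the plan adds: "The test of interest will be the within subjects factor of time, with affiliation goals expected to improve over time".

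Elsewhere the intent is comparative. Section B says that comparing the randomized ASPs "will yield preliminary data on the effectiveness of social mediators", and Section E, Secondary Aim 3 says that "the indirect effect of the program on PA through social mechanisms will be examined".

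**The concern.** Read literally, criterion 1 is met when intervention youth score higher after the program than before it. The intervention-only time effect answers exactly that question, and it is the only test singled out by name under Primary Aim 2. With two analyses planned and no rule linking either one to the criterion, the choice can be made after the results are seen.

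A change over time in one arm mixes any program effect with whatever would have happened anyway, such as season, familiarity with the questionnaires, or settling into the afterschool program. The comparison ASPs exist to remove that component. The matter goes beyond labelling: the introduction to Section E lists change in the targeted social mechanisms among the markers of program success and says the study will gauge a plausible effect size for a larger application.

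**Working it through.** The plan states no alpha, power or sample-size figure for this aim, so there is nothing of its own to reproduce. The check is mainly one of reading.

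**Passages side by side**

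- Criterion 1 (abstract; Section B): a rise from baseline to post-intervention, no comparator.
- Secondary Aims 1 and 2 (Section B): a greater gain or healthier trajectory, comparator named.
- Section E, first model: both arms included; the treatment-by-time contrast is implied by the restated aim but not named.
- Section E, second model: intervention arm only; the time effect is named as the test, with improvement expected.
- Rule linking criterion 1 to either model: none.

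**Inputs for the illustration**

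- From the documents: 3 intervention and 3 control ASPs, 200 youth (Section D, Study Design).
- Assumed: equal split, so 100 per arm and 100/3 = 33.3 per ASP; pre-post correlation r = 0.5 to 0.7; two-sided 5% level; ICC for change of 0.01 to 0.05. Covariates and the plan's second time contrast are not modeled.

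**How small a within-arm rise is enough (independent youths)**

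In baseline SD units the SD of change is sqrt(2(1-r)), and the smallest significant mean rise is t(.975, 99) × sqrt(2(1-r))/sqrt(100).

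- r = 0.5: 1.984 × 1.000/10 = 0.198 SD
- r = 0.7: 1.984 × 0.775/10 = 0.154 SD

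So an observed rise of about 0.15-0.20 SD would be significant within the arm, whatever its cause.

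**Precision of the two-arm contrast with clustering**

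The half-width is t(.975, 4) × sqrt(2) × sqrt(2(1-r))/10 × sqrt(1 + (33.3-1) × ICC), with 6 - 2 = 4 degrees of freedom at ASP level.

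- Design effects: 1 + 32.3 × 0.01 = 1.32 (square root 1.15); 1 + 32.3 × 0.05 = 2.62 (square root 1.62).
- r = 0.7, ICC 0.01: 2.776 × 1.414 × 0.0775 × 1.15 = 0.35 SD
- r = 0.5, ICC 0.05: 2.776 × 1.414 × 0.1000 × 1.62 = 0.64 SD

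For the intervention arm alone (3 ASPs, 2 degrees of freedom, no sqrt(2) factor):

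- r = 0.7, ICC 0.01: 4.303 × 0.0775 × 1.15 = 0.38 SD
- r = 0.5, ICC 0.05: 4.303 × 0.1000 × 1.62 = 0.70 SD

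Once clustering and ASP-level degrees of freedom are respected, the single-arm estimate is therefore no more precise than the controlled one.

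**The case against.** The strongest reply is that the controlled analysis is already the plan. Section E restates Primary Aim 2 in comparative terms and assesses it first with treatment in the model. The intervention-only model comes second and is introduced as a look at overall change; its named test is the test within that model. All of this stands. A reader might infer from the quoted sentence that the primary aim rests on an uncontrolled test, or that no controlled analysis is planned. The documents support neither reading.

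Three further points also stand:

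- The unnamed treatment-by-time term is not peculiar to this aim. Secondary Aims 1 and 2 use the same shorthand in Section E.
- The documents set no significance threshold for criterion 1, so treating it as passed at p<0.05 is an assumption of the illustration.
- Shared upward change is not shown. The comparison curriculum in Section D is interactive and includes self-esteem content, which makes shared change possible, but the documents give neither its size nor its direction. A downward drift would make the within-arm test conservative. A reader might want a rate of false success; any such rate would rest wholly on an assumed drift, so none is given here.

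The weekly process evaluation in Section D also looks for changes in the control condition, and criterion 1 is only one of four. Neither removes the gap: the process evaluation does not compare youth-reported change between arms, and nothing says which analysis settles the criterion.

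**Conclusion.** The point holds as an undefined decision rule. Criterion 1 is worded without a comparator, two analyses are planned, and nothing says which one decides it, so a rise shared with comparison ASPs could be counted as meeting it. The text permits that reading but does not require it.

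The size of the problem cannot be fixed from the documents. The one illustrative figure, a within-arm rise of about 0.15-0.20 SD being enough for significance, depends on 100 independent youth per arm, r of 0.5-0.7 and a two-sided 5% level. It shows only that a modest change would suffice, not that one is likely.

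A reader might also infer that moving to the randomized contrast costs precision. That is true only if youths are treated as independent; with ASP-level degrees of freedom it is not.

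**What to change.** - **Abstract and Section B, Primary Aims, item 2:** word criterion 1 as greater improvement in connectedness and affiliation orientation than comparison youth, between baseline and post-intervention.
- **Section E, Primary Aim 2:** state that criterion 1 is judged on the treatment-by-time contrast for each social mechanism measured in both conditions, reported as an estimate with a 95% CI that allows for clustering by ASP.
- **Same paragraph:** label the intervention-only time analysis descriptive, show change in both arms side by side where both are measured, and say that within-arm change is not evidence of a program effect.

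The cost is wording; no new data are needed and the two-arm model is already planned. Three things are given up or exposed. The easier, uncontrolled reading of the criterion goes. Any mechanism measured only in the intervention arm would be described and not tested. The interval will be wide, with a half-width of about 0.35-0.64 SD under the assumptions above, which is as much as six ASPs can offer and should be stated openly.
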